2.4.5.3.2 Analyses of suicidality assessment

Summaries of participants for the C-SSRS categories of suicidal ideation or suicidal behavior, and shift tables for baseline and during treatment responses will be provided.

2.4.6 Analyses of PD data

████████████████████ in case of index AEs will be reported using descriptive statistics.

[REDACTED] data will be summarized for each visit by dose group and overall using the following descriptive statistics: mean, geometric mean, median, SD, coefficient of variation, minimum, and maximum.

2.5 DATA HANDLING CONVENTIONS

2.5.1 Contingency measures for a regional or national emergency that is declared by a governmental agency

For participants in Ukraine and Russia who are impacted by the national emergency and are lost to follow-up, their data will be handled as follows:

- For the efficacy endpoint annualized adjudicated relapse rate, all observed events, if any, up to the last contact date for the participant will be included in the analysis and the observation duration will be from the first IMP in LTS16004 to the last contact date. No imputation will be performed for the unobserved events that may happen after the last contact date.
- Similarly, for the efficacy endpoint proportion of relapse-free participants, if the participant has no relapse by the last contact date, then the participant will be considered as free of relapse until that date. His/her data will be censored after the last contact date.
- For other efficacy endpoints including MRI parameters, EDSS, [REDACTED] and safety endpoints including laboratory parameters, vital signs and ECG, all observed data up to the last contact date will be included for assessment. Summary statistics will be computed based on the observed data. No imputation will be performed for data missing due to lost to follow-up.

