7.1 DISCONTINUATION OF STUDY INTERVENTION

7.1.1 Definitive discontinuation

The IMP should be continued whenever possible.

In case the IMP is stopped, it should be determined whether the stop can be made temporarily; definitive IMP discontinuation should be a last resort. Any IMP discontinuation must be fully documented in the eCRF. In any case, the participant should remain in the study as long as possible.

Definitive intervention discontinuation is any intervention discontinuation associated with the definitive decision from the Investigator not to re-expose the participant to the IMP at any time during the study, or from the participant not to be re-exposed to the IMP, whatever the reason.

Discontinuation of study intervention for abnormal liver function should be considered by the Investigator when a participant meets one of the conditions outlined in [Section 10.6](#) or if the Investigator believes that it is in best interest of the participant.

If a clinically significant finding is identified in the ECG (including, but not limited to changes from baseline in QT interval corrected using Fridericia's formula [QTcF]) after enrollment, the Investigator or qualified designee will determine if the participant can continue in the study and if any change in participant management is needed. Review of ECG findings by a cardiologist needs to be taken into consideration for a decision of a definitive discontinuation of study intervention because of ECG changes. This review of the ECG printed at the time of collection must be documented. Any new clinically relevant finding should be reported as an AE.

See the schedule of activities (SoA) ([Section 1.3](#)) for data to be collected at the time of intervention discontinuation and follow-up and for any further evaluations that need to be completed.

Any abnormal laboratory value or ECG parameter will be confirmed within 24 hours to inform the decision whether to discontinue the IMP for the concerned participant.

In case of premature discontinuation of the intervention, the end-of-treatment visit will be conducted.

Handling of participants after definitive intervention discontinuation

Participants will be followed-up according to the study procedures specified in this protocol up to the scheduled date of study completion, or up to recovery or stabilization of any AE to be followed-up as specified in this protocol, whichever comes last.

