8.1.2.2 Definition of multiple sclerosis relapse

For the purposes of this study, MS relapse is defined as acute, new neurological symptoms or worsening of previous neurological symptoms with an objective change on neurological examination. Symptoms must:

- Be attributable to MS.
- Last for ≥ 24 hours, with or without recovery.
- Be present at normal body temperature (ie, no infection, excessive exercise, or excessively high ambient temperature), and
- Be preceded by ≥ 30 days of clinical stability (including no previous MS relapse).

Note: An exacerbation or recurrence of symptoms and signs that can be reasonably attributed to transient impairment of conduction in previously demyelinated pathways due to drugs (such as rarely occurs a few hours after injection of interferon beta), raised core body temperature (the Uhthoff phenomenon), or systemic cytokine release will not be considered a relapse.

It is at the Investigator's discretion and responsibility to choose the best treatment option for any MS relapse, such as a high dose glucocorticoid treatment course.

Analysis of relapses will be detailed in the Statistical Analysis Plan.

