10.9.2 Study procedures

Procedures to be considered in the event of a regional or national emergency declared by a governmental agency:

1. New screenings during a regional or national emergency declared by a governmental agency can be performed only if allowed by local competent authorities and after Sponsor's agreement is obtained. Rescreening will be permitted when the situation normalizes and only if allowed by local competent authorities and after Sponsor's agreement is obtained.
2. If on-site visits or alternative location (out of participant's home) are not possible, all visits from Week 1 (including those planned to be done on site) will be performed at home by a trained healthcare professional and, if allowed, by local competent authorities for:
 - Treatment administration
 - Blood sampling for safety (at least hematology, hepatic function panel, coagulation panel) other safety assessment (at least serum creatinine for eGFR calculation), and pregnancy test (if applicable)
 - Measuring vital signs
 - Monitoring of injection site reactions, AEs and SAEs

The use of a local laboratory may be allowed for safety follow up in case the central lab cannot be used.

The Investigator or delegate will perform a phone-call visit at each on-site planned visit to collect safety data and concomitant treatment. All data collected remotely will be properly documented in the participant's medical record and the study CRF.

For all assessments which will not be performed remotely, the assessment windows will be extended until participants may access the site.

If on-site visit and home visit are not possible, a temporary treatment discontinuation may be considered. The Investigator or delegate will perform a phone-call visit at each on-site planned visit to collect safety data and concomitant treatment.

Contingencies implemented due to emergency will be documented in the participant's medical record.

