1.3 DETERMINATION OF SAMPLE SIZE

There are no sample size calculations for this long-term extension study.

All participants who completed the DRI15928 study were eligible for enrollment in the LTS16004 study. The Sponsor enrolled 130 participants in the DRI15928 study, 129 completed the study treatment, and 126 enrolled in LTS16004.

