2.4.4 Analysis of efficacy endpoints

The primary objective of this LTS16004 study is to evaluate safety. Efficacy data will be summarized with appropriate measures of variability.

For by visit summaries including data from DRI15928, visits during the DRI15928 period correspond to weeks on tolebrutinib treatment.

MRI variables

Number and volume of lesions will be summarized by visit using descriptive statistics in the mITT population including data from both DRI15928 and LTS16004. For parameters with a baseline value, change and/or percent change from baseline will be included. For new/enlarging T2 lesions, the values will be standardized to per month values by dividing by the number of months (4-week intervals) from the previous MRI to the current MRI. In addition, average number of lesions per scan (new Gd-enhancing T1 hyperintense and new T1 non-enhancing hypointense) or annualized rate of lesions (new/enlarging T2) will be summarized descriptively. Graphical presentations may be used to illustrate trends over time.

Values for Gd-enhancing T1 lesions will be excluded if the participant had a suspected MS relapse and was receiving systemic corticosteroids within the 30 days prior to the MRI assessment date given the short-term effects of systemic corticosteroids on Gd-enhancing lesions.

Listings of MTR recovery and number of phase rim lesions will be provided.

For each dose group and overall, the percentage of participants with no new MRI disease activity will be provided by visit.

Time course of intensity related parameters and MTR recovery will be modeled using generalized linear mixed modeling. Annualized brain volume loss will be modeled as well.

Annualized MS relapse rate

A gross estimate of ARR is the total number of relapses for participants by dose group divided by the sum of the standardized study duration for participants in the dose group.

Total number of confirmed relapses and standardized study duration will be calculated for each participant as:

- Total number of confirmed relapses is defined as number of confirmed relapses with onset between first IMP date and treatment discontinuation/completion date (same as last dose intake date) in LTS16004.
- Standardized study duration (in years) will be calculated by $(\text{last dose intake date} - \text{first IMP date} + 1) / 365.25$ in LTS16004.

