ARR will be analyzed using a negative binomial regression model in the mITT population. The model will include the total number of confirmed relapses with onset between first and last IMP doses in LTS16004 as response variable and dose group (5/60, 15/60, 30/60, and 60/60 mg) as covariate. Log transformed standardized treatment duration will be included in the model as an "offset" variable. The estimated ARR for each dose group and corresponding 95% 2-sided CI will be derived from the negative binomial model. The relative reductions in ARR (60/60 mg versus each other dose group) along with 95% CIs will be estimated from the model.

Number of participants with 0, 1, 2, 3, 4, or ≥ 5 relapses will be presented by dose group, namely, 5/60, 15/60, 30/60, and 60/60 mg.

The ARR for the tolebrutinib 60 mg treatment period will be analyzed using a negative binomial regression model, as well. Only relapses with onset during the tolebrutinib 60 mg treatment period will be counted, which means Part B only for participants originally assigned to 5, 15 and 30 mg dose groups and Parts A and B for participants originally assigned to the 60 mg dose group. Excluded are patient years and relapses during the first 8 weeks of tolebrutinib treatment after the switch to Part B for participants in the 5/15/30 to 60 mg groups and the same for participants in the 60/60 mg dose group, if the sum of the placebo run-out period (if applicable) and any gap period is >4 weeks. The negative binomial regression model will use total number of relapses as the response variable and log transformed standardized treatment duration as an "offset" variable. The estimated ARR and the 95% CI will be provided.

The number of participants with 0, 1, 2, 3, 4, or ≥ 5 relapses during the tolebrutinib 60 mg treatment period will also be presented.

Proportion of participants relapse free

Time to first confirmed relapse in LTS16004 is defined as "the date of first relapse - first IMP date (in LTS16004) + 1". If the participant has no relapse before treatment discontinuation/completion, then the participant will be considered as free of relapse until the date of treatment discontinuation/completion. His/her data will be censored after this date. The proportion of participants without confirmed relapse in LTS16004 will be estimated based on the Kaplan-Meier curve at yearly time points (1, 2, 3, 4 and 5 years since first IMP in LTS16004).

Change from baseline in EDSS scores

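### For emergency-affected Ukraine/Russia participants lost to follow-up, SAP 2.5.1 ends the relapse window at last contact even when an earlier last dose is recorded, whereas SAP 2.4.4 ends it at last dose for everyone else

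*SAP*

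**What the plan says.** SAP 2.4.4 sets the general rule. The ARR numerator is the "number of confirmed relapses with onset between first IMP date and treatment discontinuation/completion date (same as last dose intake date) in LTS16004". The denominator runs from the first to the last dose intake date, divided by 365.25, and the log of treatment duration is the offset in the negative binomial model. Relapse-free time is censored at treatment discontinuation or completion. A supplementary ARR for the 60 mg period has its own window: "Only relapses with onset during the tolebrutinib 60 mg treatment period will be counted".

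SAP 2.5.1 sets a separate rule for participants in Ukraine and Russia who are affected by the emergency and lost to follow-up. For ARR, every observed relapse up to last contact counts and "the observation duration will be from the first IMP in LTS16004 to the last contact date". For the relapse-free proportion, censoring is also at last contact. The section gives no reason for the different end date, does not mention the last dose, and plans no sensitivity analysis.

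SAP 2.5.2 takes the last-dose date from the end-of-treatment page and leaves exposure duration missing if that date is missing.

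**The concern.** Last contact can be later than last dose in two ways that the protocol provides for. After definitive discontinuation, Protocol 7.1.1 says "Participants will be followed-up according to the study procedures specified in this protocol up to the scheduled date of study completion" or until any adverse event under follow-up has resolved or stabilized, if that is later. Someone who stopped drug and was lost afterwards therefore has off-drug follow-up. In an emergency, Protocol 10.9.2 says "If on-site visit and home visit are not possible, a temporary treatment discontinuation may be considered", while phone-call visits go on. Someone who is then lost without restarting also has contact after the last dose.

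For such participants, 2.5.1 puts time and relapses after the last dose into the dose-group ARR and the Kaplan-Meier curve. A participant elsewhere who stops drug contributes nothing after the last dose. One model and one curve would then combine two risk windows, chosen by country and follow-up status, and the ARR would no longer have a single on-treatment meaning.

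Ascertainment may differ as well. Protocol 8.1.2.2 defines a relapse as "acute, new neurological symptoms or worsening of previous neurological symptoms with an objective change on neurological examination". If contact after the last dose is by phone, fewer relapses may be confirmed while the time still counts. If participants are examined, off-drug relapses are counted in their tolebrutinib dose group.

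**Working it through.** **1. The two rules side by side**

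| Element | SAP 2.4.4 (everyone else) | SAP 2.5.1 (Ukraine/Russia, affected and lost) |
|---|---|---|
| Relapses counted | onset up to last dose | all observed up to last contact |
| Time at risk for ARR | first to last dose | first dose to last contact |
| Relapse-free censoring | end of treatment | last contact |

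The rules agree when last dose and last contact coincide. They differ by the gap g when last contact is later.

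**2. Inputs**

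The documents have no figure to reproduce: "There are no sample size calculations for this long-term extension study", and no ARR or event count is stated. From the documents: N = 126 ("129 completed the study treatment, and 126 enrolled in LTS16004"), and a Month 60 target of day 1680 in SAP Table 2, so 1680/365.25 = 4.60 years. Everything else is assumed: on-drug ARR 0.20, the share affected, their years on drug, the gap, and the off-drug relapse rate.

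**3. One participant**

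Take 1 relapse and 700 days from first to last dose. By 2.4.4 the ARR is 365.25/700 = 0.522. By 2.5.1, with no further relapse, it is 365.25/(700 + g):

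- g = 84: 0.466 (-10.7%)
- g = 168: 0.421 (-19.4%)
- g = 336: 0.353 (-32.4%)

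**4. Pooled over 126 participants**

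Let P be on-drug person-years, F off-drug person-years up to last contact, and r the off-drug rate of ascertained relapses. The ARR by 2.5.1 is (0.20 × P + r × F)/(P + F). With F = 0 it is 0.20.

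Set A: unaffected participants 4.60 years each, affected participants 2 years on drug; r = 0 (none ascertained) or 0.50 (2.5 times the on-drug rate, all ascertained).

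- 5% affected, g = 84 days: P = 563.2, F = 1.4. ARR 0.1995 (-0.3%) or 0.2008 (+0.4%).
- 30% affected, g = 336 days: P = 481.3, F = 34.8. ARR 0.1865 (-6.7%) or 0.2202 (+10.1%).

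Set B: unaffected participants 4 years, affected participants 2.5 years on drug; r = 0 or 0.60 (three times the on-drug rate).

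- 10 affected, gap 0.5 year: P = 116 × 4 + 10 × 2.5 = 489, F = 5. ARR 97.8/494 = 0.198 (-1.0%) or 100.8/494 = 0.204 (+2.0%).
- 30 affected, gap 1 year: P = 96 × 4 + 30 × 2.5 = 459, F = 30. ARR 91.8/489 = 0.188 (-6.1%) or 109.8/489 = 0.225 (+12.3%).

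The extremes over both sets are -6.7% and +12.3%. SAP 2.4.4 reports ARR by dose group, and a single group could shift more than this if the affected participants cluster in it.

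**5. Against sampling error**

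With about 92 relapses (0.20 × 459), a Poisson 95% interval on the log scale is exp(±1.96/√91.8) = exp(±0.205), or -18.5% to +22.7%. Every pooled shift above lies inside it.

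**The case against.** The best defence is that the rule has a sensible purpose. People lost in an emergency are the likeliest to lack an end-of-treatment page. Without a last-dose date, 2.5.2 leaves duration missing and the model has no offset. Last contact is a natural fallback, and it ends numerator and denominator together. This stands for missing dates. The SAP does not give it as the reason, however, and 2.5.1 is not limited to missing dates.

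A reader might infer more than the documents support in four respects:

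- *That the added time is mostly off drug and by phone.* No document says how often. Protocol 6.1.1 allows direct-to-patient shipment, the schedule of activities lets M39, M45, M51 and M57 be phone contacts with drug dispensed, and 6.4 supplies drug up to the next visit. Under 10.9.2, interruption is only an option. If drug continued to last contact, the rule adds no off-drug time.
- *That no relapse can be counted in that time.* Under Protocol 8.1.2.1 a suspected relapse prompts an unscheduled visit, and the SAP counts relapses by onset date, so a later examination could still confirm one. Ascertainment may be reduced, but it need not be nil.
- *That 2.4.4 is a strictly on-drug window.* Its formula subtracts no interruptions between first and last dose, so that time already counts for everyone. Only time after the last dose is new.
- *That 2.5.1 contradicts the 60 mg ARR.* It would do so only if applied there. Its window starts at first dose in LTS16004, which cannot be the 60 mg window for participants who began on 5, 15 or 30 mg. The SAP leaves the matter unstated.

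It is also fair that the pooled shifts are smaller than sampling error, on endpoints that do not carry the primary objective. That limits the weight of the point but does not justify two windows in one model.

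**Conclusion.** The point holds in a limited form. Followed as written, 2.5.1 uses a different end of window from 2.4.4 for the relapse count, the offset and the censoring, in one subgroup, even when the last-dose date is known. It matters only for participants whose last contact is later than their last dose.

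The direction cannot be fixed from the documents. Off-drug time with relapses missed lowers the ARR and raises the relapse-free proportion, while off-drug relapses that are ascertained at a higher rate do the opposite. A claim that the rule flatters the drug would therefore go too far. The pooled range of about -7% to +12% rests wholly on the assumed inputs in both sets, and its ends need about 30 or more of the 126 affected with gaps of 11 months or more.

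ARR is a secondary endpoint, the relapse-free proportion is exploratory, the primary objective is safety and no p-values are calculated. This should be corrected before database lock as a matter of consistency. It does not threaten the study's main conclusions.

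**What to change.** In SAP 2.5.1, first and second bullets, end the window at the earlier of the recorded last-dose date and the last contact date. Use last contact alone only when the last-dose date is missing, and give the reason: 2.5.2 would otherwise leave the offset missing.

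Apply that one end date to the relapse count, the negative binomial offset and the Kaplan-Meier censoring. State that the 60 mg ARR keeps its own 60 mg window, closed by the same end date. List relapses with onset after the last dose separately. The last-contact version can be kept as a sensitivity analysis.

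The cost is a short SAP edit, one derived date and one listing. The small downside is that some off-drug contact time no longer contributes to the ARR. No observed relapse goes unreported.

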2.5.2 Missing data

For categorical variables, participants with missing data are not included in calculations of percentages unless otherwise specified. When relevant, the number of participants with missing data is presented.

Handling of computation of treatment duration if IMP end-of-treatment date is missing

For the calculation of the treatment duration, the date of the last dose of IMP is equal to the date of last administration reported on the end-of-treatment CRF page. If this date is missing, the exposure duration should be left as missing.

The last dose intake should be clearly identified in the CRF and should not be approximated by the last returned package date.

Handling of concomitant medication missing/partial dates

No imputation of medication start/end dates or times will be performed.

Handling of AEs with missing or partial date/time of onset

Missing or partial AE onset dates and times will be imputed so that if the partial AE onset date/time information does not indicate that the AE started prior to treatment or after the TEAE period, the adverse event will be classified as treatment emergent. No imputation of adverse event end dates/times will be performed. These data imputations are for categorization purpose only and will not be used in listings. No imputation is planned for date/time of adverse event resolution.

Handling of missing assessment of relationship of adverse events to investigational medicinal product

If the assessment of the relationship to IMP is missing, then the relationship to IMP has to be assumed and the adverse event considered as such in the frequency tables of possibly related adverse events, but no imputation should be done at the data level.

Handling of missing intensity/severity of adverse events

If the intensity is missing for one of the treatment-emergent occurrences of an AE, the maximal intensity on the remaining occurrences will be considered. If the intensity is missing for all the occurrences, a “missing” category will be added in the summary table. This does not apply for events for which intensity is not collected in the eCRF, ie, overdose and pregnancy.

Handling of potentially clinically significant abnormalities

If a participant has a missing baseline he will be grouped in the category “normal/missing at baseline.”

For PCSAs with 2 conditions, one based on a change from baseline value or a normal range and the other on a threshold value, with the first condition being missing, the PCSA will be based only on the second condition.

For a PCSA defined on a threshold and/or a normal range, this PCSA will be derived using this threshold if the normal range is missing, eg, for eosinophils the PCSA is >0.5 GIGA/L or $>\text{ULN}$ if $\text{ULN} \geq 0.5$ GIGA/L. When ULN is missing, the value 0.5 should be used.

Measurements flagged as invalid by the laboratory will not be summarized or taken into account in the computation of PCSA values.

